### 5.1 INCLUSION CRITERIA

Eligible subjects must meet all the following inclusion criteria to be eligible for study participation:

1. Male or female adults, age 22 years or older at the Preoperative Visit.
2. Clinically significant cataract in the study eye eligible for standard phacoemulsification cataract surgery.
3. Eligible for receipt of an IOL power within the range of the investigational IOL in the study eye. **(The Investigational IOL is available in powers from +15 D to +30 D Spherical Equivalent)**
4. Pre-operative corneal astigmatism in the range:  $\geq 0.75$  D and  $\leq 1.50$  D in the study eye
6. Clear intraocular media other than cataract in the study eye.
7. Best corrected visual acuity equal to or worse than 0.3 logMAR, with or without a glare source in the study eye.
8. Ability to dilate pupil sufficiently (greater than or equal to 6.0 mm) to allow visualization of Toric IOL axis markings post-implantation in the study eye.
9. Projected BCDVA of 0.2 logMAR (20/32 Snellen) or better in the study eye after cataract surgery/IOL implantation, as determined by the medical judgment of the Investigator.

10. Contact lens users must be willing to discontinue wear of their lenses in the study eye in accordance with the following requirements:
  - i. Rigid gas permeable and toric lenses for  $\geq 7$  days prior to the Preoperative Visit
  - ii. Soft non-toric contact lenses for  $\geq 3$  days prior to the Preoperative Visit
  - iii. All contact lens wearers must demonstrate a stable refraction within  $\pm 0.50$  D MRSE and 15 degrees astigmatic axis on two consecutive examinations at least 1 week apart in an eye to be treated.
11. Provide signed written consent prior to participation in any study-related procedures.
12. Ability, comprehension, and willingness to follow study instructions, and to complete all study visits.
13. Female subjects must be 1-year postmenopausal, surgically sterilized, or, if of childbearing potential, have a negative urine pregnancy test at the Preoperative Visit. Women of childbearing potential must use an acceptable form of contraception throughout the study. Acceptable methods include at least one of the following: intrauterine (intrauterine device), hormonal (oral, injection, patch, implant, ring), barrier with spermicide (condom, diaphragm), or abstinence.

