### 8.1 PREOPERATIVE VISIT (DAY -90 TO DAY -1)

The Preoperative Visit must occur no more than 90 days and no less than 1 day prior to the Operative Visit. Informed consent must be obtained prior to performing study-specific procedures not part of the

investigator's routine standard of care. Subjects who sign the ICF will be given a unique 5-digit screening number, where the first two digits correspond to the site number.

At this visit, the following activities will be performed:

1. Biometrya
  - Keratometry\*
  - Target refraction\*
  - IOL power calculation\*
  - Axial length\*
  - Anterior chamber depth\*
  - Toric Power calculation
2. Corneal Topography\*
3. Inclusion/Exclusion Criteria Evaluation
4. Demographics
5. Concomitant Medications
6. Ocular and Significant Non-ocular Medical History\*
7. Urine Pregnancy Test (if applicable)
8. Manifest Refraction (ETDRS) – 4 m\*
9. BCDVA - Photopic, Monocular (ETDRS) – 4 m\*
10. UCDVA - Photopic, Monocular (ETDRS) – 4 m\*
11. Projected Visual Acuity\*
12. Slit lamp Examination\*
13. Intraocular Pressure\*
14. Dilated pupil size\*
15. Dilated Fundus Exam\*
16. Randomization
17. Adverse Events

*\* These assessments, if performed during routine standard of care exams up to 90 days before the subject Preoperative Visit, may be used as qualifying preoperative assessments prior to consent. All study specific evaluations not included in a routine cataract evaluation must be performed in the preoperative time period (Day -90 to Day -1).*

*a Biometry (if not done during routine standard of care exams), to be done before inclusion/exclusion criteria evaluation.*

Subjects must be targeted as closely as possible to emmetropia. **For PODEYE TORIC IOL, SRK/T formula and A-constant 119.4 should be used to determine IOL power.** Surgeons may use their personalized A-constant for model SA60AT.

The SIA value an investigator will use in this study must be a predetermined single value (each investigator may use their own personal SIA value) that is reported to the sponsor at the beginning of the study and consistently used for all subjects treated by the investigator.

The subjects will be randomized in 1:1 ratio to either Study arm or control arm, as per the randomization schedule.

## 8.2 OPERATIVE VISIT (DAY 0): FORM 0

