6.3 INCLUSION CRITERIA

Eligible subjects must meet all the following inclusion criteria to be eligible for study participation:

1. Male or female adults, age 22 years or older at the Preoperative Visit.
2. Clinically significant cataract in the study eye eligible for standard phacoemulsification cataract surgery.
3. Eligible for receipt of an IOL power within the range of the investigational IOL in the study eye. **(The Investigational IOL is available in powers from +15 D to +30 D Spherical Equivalent)**
4. Pre-operative corneal astigmatism in the range: ≥ 0.75 D and ≤ 1.50 D in the study eye
6. Clear intraocular media other than cataract in the study eye.
7. Best corrected visual acuity equal to or worse than 0.3 logMAR, with or without a glare source in the study eye.
8. Ability to dilate pupil sufficiently (greater than or equal to 6.0 mm) to allow visualization of Toric IOL axis markings post-implantation in the study eye.
9. Projected BCDVA of 0.2 logMAR (20/32 Snellen) or better in the study eye after cataract surgery/IOL implantation as determined by the medical judgment of the Investigator.
10. Contact lens users must be willing to discontinue wear of their lenses in the study eye in accordance with the following requirements:
 - i. Rigid gas permeable and toric lenses for ≥ 7 days prior to the Preoperative Visit
 - ii. Soft non-toric contact lenses for ≥ 3 days prior to the Preoperative Visit
 - iii. All contact lens wearers must demonstrate a stable refraction within ± 0.50 D MRSE and 15 degrees astigmatic axis on two consecutive examinations at least 1 week apart in an eye to be treated.
11. Provide signed written consent prior to participation in any study-related procedures.
12. Ability, comprehension, and willingness to follow study instructions, and to complete all study visits.
13. Female subjects must be 1-year postmenopausal, surgically sterilized, or, if of childbearing potential, have a negative urine pregnancy test at the Preoperative Visit. Women of childbearing potential must use an acceptable form of contraception throughout the study. Acceptable methods include at least one of the following: intrauterine (intrauterine device), hormonal (oral, injection, patch, implant, ring), barrier with spermicide (condom, diaphragm), or abstinence.

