7.2 VISIT WINDOW

The visit schedule and the visit window for each visit are outlined in **Table 1**. The visit schedule applies to all subjects in both test and control groups.

Table 1 VISIT SCHEDULE

Visit	Visit Window
Preoperative	1 to 90 days prior to surgery in the study eye
Form 0 (Operative)	Day 0
Form 1	1 to 2 days following surgery in the study eye
Form 2	7 to 14 days following surgery in the study eye
Form 3	30 to 60 days following surgery in the study eye
Form 4	120 to 180 days following surgery in the study eye

Unscheduled visits will occur as needed, due to an ocular intervention or a subject complaint regarding their eye. Recommended assessments at unscheduled visits are listed in Section 8.4 of the study protocol. In the event of missing data at a scheduled visit, unscheduled visit results within the visit window will be used as replacements for any uncollected data. If more than one unscheduled visit falls within the window, then the unscheduled visit closest to the target date will be used. If two visits are equidistant from the target, then the latter of the two will be selected.

A summary of all examinations required at each visit is provided in the schedule of activities in Appendix A.

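### The contact-lens washout is counted back from the Preoperative Visit, but the keratometry, topography and refraction it protects may be taken up to 90 days before that visit.

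*Protocol*

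**What the plan says.** Item 10 of the inclusion criteria (Protocol 5.1, repeated in the synopsis and in SAP 6.3) opens "Contact lens users must be willing to discontinue wear of their lenses in the study eye". It then sets the intervals: "Rigid gas permeable and toric lenses for ≥ 7 days prior to the Preoperative Visit", and at least 3 days for soft non-toric lenses, counted from the same visit. Item 10.iii adds that wearers must show a stable refraction (MRSE within 0.50 D, axis within 15 degrees) on two examinations at least a week apart.

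On timing, Protocol 8.1 states "The Preoperative Visit must occur no more than 90 days and no less than 1 day prior to the Operative Visit". Its list of assessments marks some with an asterisk, among them keratometry, IOL power calculation, "Corneal Topography" and "Manifest Refraction (ETDRS) – 4 m". The footnote says that starred tests, "if performed during routine standard of care exams up to 90 days before the subject Preoperative Visit, may be used as qualifying preoperative assessments", and it allows this before consent. "Toric Power calculation" carries no asterisk.

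SAP Table 1 gives the preoperative window as "1 to 90 days prior to surgery in the study eye".

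**The concern.** A washout rule exists because lens wear can alter the corneal and refractive readings. It does its job only if the lens-free days come before the reading that is used. Here the lens-free days are tied to a visit, and the readings are allowed to be older than that visit.

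Preoperative keratometry carries a good deal of weight in this trial. It decides whether the eye falls in the 0.75 to 1.50 D range, feeds the toric calculation, defines the cylinder strata, and is the baseline for surgically induced change (Protocol 9.11, SAP 8.4.4). Protocol 2.3.1 itself names inaccurate keratometry as a cause of toric misalignment.

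The co-primary endpoints would not all register such an error. Protocol 9.5 describes co-primary 3 as misalignment relative to the planned axis. A lens sitting exactly on a badly planned axis would count as a success there and would show only as residual cylinder in co-primary 1.

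**Working it through.** **1. The plan's own window arithmetic.** The synopsis puts participation at about 9 months from the Preoperative Visit to Form 4. The visit may be 90 days before surgery and Form 4 up to 180 days after: 90 + 180 = 270 days = 9.0 months of 30 days. The figure reproduces. It starts at the visit, so it does not include the look-back.

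**2. Age of a qualifying measurement.** Look-back 90 days + visit to surgery 90 days = 180 days before surgery.

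**3. Gap between measurement and washout.** With the minimum washout, a measurement can precede the first required lens-free day by up to 90 − 7 = 83 days (rigid or toric lenses) or 90 − 3 = 87 days (soft). For example, take keratometry at Day −120, a visit at Day −40 and a rigid lens left out from Day −47. The look-back is 80 days, which is allowed, and the reading precedes the washout by 73 days.

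**4. Do other visible rules close the gap?**
- *Item 10.iii* compares two refractions. It sets no limit on keratometry or cylinder magnitude, tolerates 15 degrees of axis change, and does not say that either refraction must follow lens-free days. It helps if the two examinations straddle the washout.
- *Exclusion 13* rejects a vector difference above 0.50 D between biometer and topographer. If both readings come from one lens-wearing day, a distortion common to both passes.
- *Eligibility recheck at surgery* (Protocol 8.2): the Schedule of Activities lists no keratometry or topography at Form 0.
- *SAP 8.3.1* lets a later presurgical value replace an earlier one, but only if one is taken.
- *Toric calculation*: unstarred, so done between Day −90 and Day −1, but its keratometry input is starred and may be older.

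**5. Effect on one toric eye.** Let C = 1.03 D (lens cylinder at the corneal plane, Protocol Table 1), A = corneal cylinder and θ = axis error. The residual is R = √(A² + C² − 2AC cos 2θ), which reduces to 2C sin θ when A = C. The documents give no size for a lens-induced axis shift, so 5 to 15 degrees is an assumption.

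| A (D) | θ = 0° | 5° | 10° | 15° | Added at 5°, 10°, 15° |
|---|---|---|---|---|---|
| 0.75 | 0.28 | 0.32 | 0.41 | 0.53 | 0.04, 0.13, 0.25 |
| 1.03 | 0.00 | 0.18 | 0.36 | 0.53 | 0.18, 0.36, 0.53 |
| 1.25 | 0.22 | 0.30 | 0.45 | 0.63 | 0.08, 0.23, 0.41 |
| 1.50 | 0.47 | 0.52 | 0.64 | 0.80 | 0.05, 0.17, 0.33 |

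The matched case (1.03 D) gives the largest added residual of the four.

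**6. Effect on the toric-arm mean.** The share of contact-lens wearers is not stated; 5 to 15% is assumed. Of the 115 test eyes in SAP 6.2 that is about 6 to 17 (5.75 and 17.25). If every one were affected, and at the matched value, the mean would rise by 0.05 × 0.18 = 0.01 D at the low end and 0.15 × 0.53 = 0.08 D at the high end.

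**The case against.** Several points stand against a stronger claim.

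- *No conflict with the SAP.* A reader might infer that the 180-day allowance contradicts SAP Table 1, or that SAP 7.2.1 would class old keratometry as a missed visit. It does not. Table 1 windows the Preoperative Visit exactly as Protocol 8.1 does, and the footnote is an explicit exception for standard-of-care results. SAP 8.3.1 defines baseline as preoperative, with no day limit. SAP 7.2.1 leads to imputation, which SAP 8.4.3 applies to co-primary data missing at Form 4. It follows that the documents give no ground for requiring keratometry between Day −90 and Day −1 in every subject, and no harm is shown for people who do not wear lenses.
- *Not all the text is visible.* Inclusion item 5 and parts of Protocol 8.2 are not visible, and examination methods are in a Manual of Procedures that is not part of these documents. Any of these could require lens-free keratometry. Nor do the documents say that routine biometry is done on a lens-wearing day; they only fail, in what can be read, to prevent it.
- *Partial safeguards exist.* Besides item 10.iii and exclusion 13, irregular corneal astigmatism and corneal irregularity are exclusions. Some affected eyes would be caught.
- *Direction and visibility.* A wrong planned axis adds residual cylinder only in the toric arm, so it works against the test lens and cannot create a false finding of superiority. Keratometry is repeated at Forms 3 and 4, and the error in predicted astigmatism and axis is to be summarised. That would show a planning error in part, though mixed with true surgical change.

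All of this limits the size of the point and confidence in it. None of it places the lens-free days before the measurement.

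**Conclusion.** The washout anchor does not match the measurements it is meant to protect, and on the visible text the rule can defeat its own purpose in contact-lens wearers. That much follows from the wording alone.

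The consequence is mainly for individual eyes and for the validity of their baseline. Under the assumed 5 to 15 degree error, an affected toric eye with 1.03 D of corneal cylinder keeps 0.18 to 0.53 D. At 1.50 D the added residual is 0.05 to 0.33 D.

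Two stronger readings should be avoided. One sets 0.53 D against the 0.4 D between-arm goal and concludes that co-primary 1 is in danger. That compares one eye with an arm difference; the toric-arm mean would move by at most about 0.01 to 0.08 D even if every assumed wearer were affected. The other takes 5 to 15% of all 230 subjects (12 to 35) as the number at risk. The control lens has no axis, so the axis error concerns about 6 to 17 toric eyes at most.

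Severity is minor to moderate. Confidence is medium, because the share of wearers and the size of the shift are assumptions and unseen text may already contain a rule.

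**What to change.** Keep the stated 7-day and 3-day intervals and change only the point they are counted from. In inclusion item 10 (Protocol synopsis and 5.1, SAP 6.3), count them back from the date of each qualifying keratometry, biometry, topography and refraction, including any standard-of-care measurement used under Protocol 8.1. The refractions used for item 10.iii should follow the same anchor.

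Add one sentence to the Protocol 8.1 footnote: for a contact-lens wearer whose lens-free days before a standard-of-care measurement are not documented, the measurement taken at the Preoperative Visit is the one used for eligibility and for the toric calculation. If the Manual of Procedures already requires this, a cross-reference is enough.

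The cost is short wording changes and a repeat non-contact measurement for some lens wearers, at a visit where these tests are already scheduled. Subjects who do not wear contact lenses are unaffected, and SAP 7.2 needs no change.

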### 5.3 REASONS NOT TO IMPLANT A STUDY IOL

At the time of cataract surgery, but prior to IOL implantation there are intraoperative adverse events that may prevent implantation of the designated IOLs for this clinical study. These criteria include, but are not limited to:

- 1) Intraoperative complications during phacoemulsification that require any other additional procedures or further intervention, e.g., vitrectomy.
- 2) Significant detachment of Descemet's membrane
- 3) Significant corneal endothelial damage
- 4) Wound burn
- 5) Capsular tear, iris incarceration or damage, posterior capsular rupture, vitreous loss or prolapse, or zonular weakness, dehiscence or rupture
- 6) Significant anterior chamber bleeding
- 7) Excessive iris mobility or need for iris manipulation
- 8) Mechanical or surgical manipulation required to enlarge the pupil prior to or at IOL implantation
- 9) Other ocular conditions or complications that could compromise IOL stability
- 10) Bag sulcus, sulcus-sulcus or unknown placement of haptics
- 11) Any method of anterior capsulotomy other than circular continuous curvilinear capsulorhexis (e.g., anterior capsular tears or any areas of 'can-opener' capsulotomy or FLACS)
- 12) Capsular fibrosis or other opacity
- 13) Optic and/or haptic damage/amputation
- 14) Inability to fixate IOL in desired position

If an operative adverse event prevents implantation of the investigational IOL and the IOL did not touch the eye, the subject should be implanted with an approved non-study IOL instead and followed until resolution or stability of that adverse event before discontinuation from the study. Later, the subject should be followed under the Investigator's normal standard of care.

If an operative adverse event prevents implantation of the investigational IOL and the IOL touched the eye, the subject should be implanted with an approved non-study IOL (if applicable). The Investigator should follow the subject through resolution of any adverse events (AEs) and then discontinue the

subject, followed under the Investigator's normal standard of care. In this case, the subject will be included in the Safety population.

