## 7 PARTICIPANT DISCONTINUATION/ WITHDRAWAL

### 7.1 PARTICIPANT DISCONTINUATION/ WITHDRAWAL FROM THE STUDY

Discontinued subjects are those who withdraw from the study after the study informed consent document is signed and before the final visit is completed. Subjects who sign the study consent document but fail to meet eligibility criteria or withdraw prior to randomization shall be considered discontinued due to screen failure.

A subject may be discontinued prior to the final study visit for any of the following reasons, including but not limited to:

- Screen failure
- Adverse event(s); note that subjects should be followed within the study until adverse event resolution or stability

- Investigator's request (medical decision to ensure patient safety)
- Voluntary withdrawal (subject's request)
- Death
- Study terminated by Sponsor
- Loss to follow-up

Prior to discontinuing a subject, every effort should be made to contact the subject to schedule a final study visit and obtain as much follow-up data as possible. Discontinued subjects should thereafter be followed outside of the study protocol according to the Investigator's normal standard of care.

The reason for participant discontinuation or withdrawal from the study will be recorded on the Exit Case Report Form (CRF).

Randomized subjects who do not receive a study IOL or who receive a study IOL and are discontinued or withdraw from the study afterwards will not be replaced.

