At the Operative Visit, prior to surgery, subjects will be assessed to reconfirm eligibility and any changes in concomitant medications and medical/ocular conditions will be recorded on the appropriate CRF. If the subject is determined no longer to be eligible, he/she will be discontinued from the study prior to cataract surgery.

All cataract surgical procedures will be performed by a qualified Investigator according to the Investigator's usual standard of care, using a phacoemulsification system adjusted according to the Investigator's customary settings. Surgery may be performed under either local or topical anesthesia, with or without intracameral ophthalmic anesthesia. Subjects must be targeted as closely as possible for emmetropia. Surgeons may use their personalized A-constant for model SA60AT. For PODEYE TORIC, surgeons must use the SRK/T formula and an A-constant of 119.4. The Investigator must also reference the Directions for Use for the PODEYE TORIC IOL and AcrySof SA60AT Monofocal IOL.

[REDACTED] must be used to implant the PODEYE TORIC in accordance with [REDACTED]. A qualified delivery system should be used for the AcrySof SA60AT IOL, in accordance with the Alcon Directions for Use.

[REDACTED]

[REDACTED]

No additional refractive procedures are to be performed during the operative procedure or throughout the postoperative study period. Femtosecond laser-assisted cataract surgery (FLACS) must not be performed to create corneal incisions, to adjust astigmatism during the study period, or for any other reason. (Note: Corneal incisions intended to reduce corneal astigmatism (e.g., Limbal relaxing incisions and astigmatic keratotomy are not permitted)

If operative complications prevent implantation of the investigational Study IOL (PODEYE TORIC or Control IOL) (see Section 5.3 – Reasons Not to Implant a Study IOL), a non-study IOL may be implanted instead. Subjects who were not exposed to the study IOL will be exited from the study and followed per the investigator's standard of care.

The Investigator should refer to the Manual of Procedures for more detailed guidance on PODEYE TORIC and AcrySof SA60AT implantation.

After the operative procedure but at the same visit, IOL axis orientation retro-illuminated slit lamp images must be taken for the subjects implanted with PODEYE TORIC IOL. Refer to the Manual of Procedures for more guidance.

## 8.3 POSTOPERATIVE VISITS: FORM 1 THROUGH FORM 4

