#### 8.6.1 IOL EXCHANGE

An IOL exchange, where the IOL is replaced with the same lens model, is only allowed at the Operative visit (Form 0). If the IOL needs to be replaced sometime later after the operative visit, the replacement IOL cannot be the investigational IOL model.

---

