### 9.2 ANALYSIS POPULATIONS

The All-enrolled population includes all subjects who sign an informed consent form. This population will be used for disposition summaries.

The Safety population will include all subjects where the test or control IOL touched the eye.

The intent to treat (ITT) population includes all randomized subjects. Missing data will be imputed. Subjects will be analyzed as randomized. The ITT population is the primary analysis population for assessing effectiveness.

The All-implanted population includes all ITT subjects who were successfully implanted with one of the two study IOLs and who attended at least one postoperative visit. Missing data will be imputed. Subjects will be analyzed as randomized. The All-implanted population is supportive of the ITT population for assessing effectiveness.

The Per-Protocol (PP) population includes all subjects in the All-implanted population who have no major protocol deviations that could affect the interpretation of effectiveness. Exclusions from PP will be determined prior to study unmasking. Missing data will not be imputed. Subjects will be analyzed as treated. Analyses based on PP will be supportive of those based on ITT.

The Best-Case Set will include subjects in PP with all of the following characteristics:

- No major protocol deviations potentially affecting any of the primary effectiveness endpoints (BCDVA, DCNVA). Major protocol deviations that may potentially affect the primary effectiveness endpoints include, but are not limited to:
  - Inclusion of ineligible subjects
  - Implantation of incorrect IOL
  - Missed assessments for effectiveness endpoints at Form 4
  - Receipt of medication likely to interfere with visual performance at Form 4
- At least one eye implanted with a study lens
- No clinically significant preoperative ocular pathology in the first operative eye, including any of the following present prior to the operative visit
  - Pseudoexfoliation
  - Glaucoma
  - Uveitis
  - Retinal detachment
  - Diabetic retinopathy
  - Macular degeneration
  - Amblyopia
  - Other preoperative pathologies that are likely to affect central acuity
- No macular degeneration detected at any time in the first operative eye
- No previous surgery for the correction of refractive errors in the first operative eye

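### Follow-up rules for an unimplanted or damaged study lens need reconciling, and randomized subjects without the study lens leave before Form 4 although ITT is primary and their cylinder could be measured.

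*Protocol*

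**What the plan says.** **Lens never touched the eye.** Protocol Section 5.3 has the subject receive an approved non-study lens and be "followed until resolution or stability of that adverse event before discontinuation from the study". Section 7.1, under discontinuation for adverse events, agrees: "note that subjects should be followed within the study until adverse event resolution or stability". Section 8.2 says that "a non-study IOL may be implanted instead", then adds: "Subjects who were not exposed to the study IOL will be exited from the study and followed per the investigator's standard of care". It attaches no adverse-event condition to that exit.

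**Lens touched the eye but was not implanted.** Section 5.3: "The Investigator should follow the subject through resolution of any adverse events (AEs) and then discontinue the" subject, who is counted in the Safety population. The exit sentence in Section 8.2 covers only unexposed subjects, so the two sections do not conflict here.

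**Lens damaged.** Item 13 of the Section 5.3 list reads "Optic and/or haptic damage/amputation". Section 8.6.1 states: "An IOL exchange, where the IOL is replaced with the same lens model, is only allowed at the Operative visit (Form 0"). Neither refers to the other.

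**Analysis.** Protocol Section 9.2 defines ITT as all randomized subjects, analysed as randomized, and states: "The ITT population is the primary analysis population for assessing effectiveness". SAP Sections 7.1 and 8.4 agree. Protocol Section 7.1 says that randomized subjects who do not receive a study lens are not replaced. SAP Section 8.4.3 imputes missing Form 4 values. The predictors it names are attempted toric correction, age and sex; some of the surrounding text is redacted.

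**The concern.** There are two separate matters.

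The first is operational. A site that reads Section 8.2 on the day of surgery could exit an unexposed subject with an open surgical complication, while a site that reads 5.3 or 7.1 would keep the same subject under study follow-up. Unexposed subjects are also outside the Safety population, which requires that the lens touched the eye, and SAP Appendix B bases the safety tables on that population. The adverse-event record is therefore the main trace of such a complication. For a damaged lens, one site may discontinue the subject and another may exchange the lens and keep the subject.

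The second concerns the estimate. A randomized subject who ends surgery with a non-study lens is discontinued before Form 4 but remains in ITT. The value for co-primary 1 (residual manifest cylinder) must then be imputed, although manifest refraction can be done in an eye with any lens. If the imputation model does not know which lens was received, a toric-arm eye holding a non-toric lens may be given a cylinder typical of toric-corrected eyes, which favours the test lens.

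**Working it through.** **Step 1. The instructions side by side.**

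| Case | Section 5.3 | Section 8.2 | Other sections |
|---|---|---|---|
| Lens did not touch the eye | Follow until the event resolves or is stable, then discontinue | Exit to standard of care; no event condition | 7.1 agrees with 5.3; 8.7.5 asks that events open at exit be followed |
| Lens touched the eye, not implanted | Follow through resolution, then discontinue | Exit sentence does not apply | No conflict |
| Optic or haptic damaged | Listed as a reason not to implant | Refers to 5.3 | 8.6.1 allows same-model exchange at Form 0 |

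There are two smaller mismatches. Section 5.3 says a non-study lens should be used, whereas 8.2 says it may be. The non-study-lens routes in 5.3 name only the investigational lens, whereas 8.2 names both study lenses.

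**Step 2. Which mismatch changes whether a Form 4 value exists?** For a lens that is not implanted, 5.3 and 8.2 both end in discontinuation before Form 4. Making them agree recovers no refraction. Only the damaged-lens case (discontinue under 5.3, stay under 8.6.1) changes whether an outcome is observed. The missing ITT values arise mainly from the discontinuation rule itself.

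**Step 3. The plan's own figures.** Joint power: 0.94 × 0.99 × 0.99 × 0.99 = 0.912, matching the stated 91%. Completers: 230 × (1 − 0.13) = 200.1, matching the stated 200. Both documents treat randomized and implanted as one number (230) and place dropout after implantation. No allowance for randomized but unimplanted subjects is visible, though parts of those sentences are redacted.

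**Step 4. Number of eyes (assumed rate).** The documents give no non-implantation rate. Taking 1% to 5%: 230 × 0.01 = 2.3 and 230 × 0.05 = 11.5 eyes, or about 1 to 6 per arm of 115. One eye is 1/115 = 0.87% of an arm.

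**Step 5. Shift in the mean difference.** Let k toric-arm eyes hold a non-toric lens and be imputed as if toric-corrected, each wrong by d on average. Shift = k × d / 115.

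- With d = 0.4 D (the performance goal used as the average error): k = 1 gives 0.003 D; k = 3 gives 0.010 D; k = 6 gives 0.021 D.
- Ceiling, with d = 1.03 D (the corneal-plane cylinder in Protocol Table 1): 6 × 1.03 / 115 = 0.054 D, or about 13% of the 0.4 D goal (0.054/0.4).

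**Step 6. Power.** The SD for co-primary 1 is redacted, so it was solved from power = Φ(0.4 / (SD × √(2/n)) − 1.96) with 94% at n = 100 per arm, giving SD ≈ 0.805 D. Removing eyes from each arm:

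| Eyes lost per arm | Co-primary 1 power | Joint power |
|---|---|---|
| 0 | 94.0% | 91.2% |
| 1 | 93.8% | 91.0% |
| 3 | 93.3% | 90.6% |
| 6 | 92.6% | 89.9% |

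If co-primary 1 starts from 99% (94% plus the 5% Wilcoxon allowance in Protocol Section 9.8), power with 6 lost per arm is still 98.6%. One-sided versions differ by at most 0.2 points.

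**The case against.** The strongest reply is that adverse-event follow-up is already required in three places. Sections 5.3 and 7.1 say so, and 8.7.5 requires documentation until recovery and follow-up of events open at exit. Section 8.2 refers to 5.3 in the sentence before the exit rule and gives no time of exit, so it can be read as shorthand for 5.3. A reader might infer that 8.2 stops adverse-event follow-up on Day 0; the documents do not go that far. What stands is that 8.2 omits a condition that 5.3 and 7.1 state, and that 8.7.5 does not say the follow-up takes place within the study.

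On the damaged lens, 5.3 speaks of events that may prevent implantation, and its non-study-lens route starts only when implantation was in fact prevented. A damaged lens exchanged for the same model need not count as prevented. That reading is fair. However, items 10 and 14 of the list, and the branch for a lens that touched the eye, also describe a lens already in the eye, so 5.3 and 8.6.1 overlap. Sites may handle the case differently; it does not follow that they will. Redacted paragraphs in 8.2 and the Manual of Procedures may hold a linking rule.

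On imputation, the tipping-point analysis for co-primary 1 in Protocol Section 9.7 starts with missing toric eyes at the worst observed value and missing control eyes at the best. That partly probes this concern. It moves all missing eyes together and cannot recover a value that could have been measured.

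**Conclusion.** Both points hold, and they should be kept apart. The wording of 5.3, 7.1, 8.2, 8.6.1 and 8.7.5 needs reconciling. Independently, the visible plan discards a measurable co-primary 1 outcome for randomized subjects who do not receive or retain the study lens, while keeping them in the primary population.

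The size is small. At an assumed 1% to 5% non-implantation, the mean difference shifts by about 0.003 to 0.021 D, with a ceiling of about 0.05 D, and co-primary 1 power falls by about 0.2 to 1.4 points. These figures assume that the replacement lens is non-toric and that the imputation treats the eye as toric-corrected. The redacted SAP text could change the second assumption. The gain is in ITT integrity and adverse-event follow-up rather than power.

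Three stronger readings are not supported. A reader might infer that the conflict between sections causes the ITT loss; it does not, because 5.3 and 8.2 both end in discontinuation. A reader might take 1.03 D as the bias; it is a per-eye maximum. A reader might also infer that surgeons, who are not among the masked roles in Section 6.3, would treat the arms differently. The documents give no evidence of that, and 8.2 names both lenses.

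**What to change.** 1. Reconcile Protocol Sections 5.3, 7.1, 8.2, 8.6.1 and 8.7.5 into one rule for each case (lens not in contact, lens in contact but not retained, lens damaged), with one adverse-event follow-up requirement that applies to both arms. The sponsor decides the content.
2. In Sections 7.1 and 8.2, separate not receiving or retaining the study lens from withdrawing from the study. Ask willing subjects in the first group to attend Form 4 for manifest refraction, BCDVA and adverse events.
3. In SAP Section 8.4.3, state that the measured Form 4 cylinder of these subjects is used for co-primary 1 in ITT, analysed as randomized. For those who decline, state how the lens received is taken into account. This concerns co-primary 1 only: co-primaries 3 and 4 are axis outcomes of the toric lens and cannot be measured in an eye without it.

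The cost is protocol and SAP wording and one Form 4 visit for a few subjects (about 1 to 6 per arm under the assumed rates). The co-primary 1 result may become slightly less favourable to the test lens.
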